# 7.2.5.3 Recording instructions for adverse events

Each subject should be questioned about AEs at each study visit following the screening visit. All AEs, non-serious as well as serious, are to be reported as an AE in the eCRF.

The question asked should be: "Since your last clinical visit; have you had any health problems?". Information on AEs can also be obtained from signs and symptoms detected during each examination or from a laboratory test, observations made by the study center personnel, subject diaries, or spontaneous reports from the subjects or their relatives.

When an AE is related to a device deficiency (refer to Section 7.2.10), including technical device malfunction, the AE shall be recorded on the AE form/module in the eCRF and the technical complaint shall be reported separately on the clinical study complaint form, provided in the investigator file, and in the eCRF.

Investigators, or other study center personnel, shall record all AEs in the eCRF, including:

- a) Event term (recorded in standard medical terminology and avoiding abbreviations)
- b) Affected area
- c) Start date (first day with symptoms)
- d) Stop date (last day with symptoms)
- e) Intensity (mild, moderate, or severe according to definition in Section 7.2.5.4)
- f) Seriousness (serious or not serious, according to definition in Section 7.2.5.2)
- g) Causal relationship to study product or study product injection procedure (yes or no)
- h) Action taken (none, medication treatment, non-pharmacological treatment, or other procedures/tests, subject withdrawn)
- i) Outcome of the AE (ongoing, recovered, recovered with sequelae, death, chronic/ stable, not recovered at the end of the study)

The AE form/module in the eCRF must be signed and dated by the Investigator.

<sup>II The term "life-threatening" in the definition of "serious" refers to an event in which the patient was at risk of death at the time of the event; it does not refer to an event which hypothetically might have caused death if it were more severe. (Source: ICH-E2A clinical safety data management: definitions and standards for expedited reporting).

III Planned hospitalization for a pre-existing condition, or a procedure required by the CSP, without serious deterioration in health, is not considered a SAE. (Source: ISO14155:2011).

2021-08-25 16:18

The pre-defined, expected post-treatment events shall be assessed separately, see Section 7.2.1. These events shall be collected daily by subjects in a diary for 28 days following each treatment.

## 7.2.5.3.1 Intensity

All AEs, non-serious as well as serious, are to be reported as an AE in the eCRF.

Intensity will be recorded for each reported AE. The following definitions of intensity are to be used:

Mild: Awareness of symptoms or signs, but easily tolerated (acceptable)

**Moderate:** Enough discomfort to interfere with usual activity (disturbing)

**Severe:** Incapacity to work or to do usual activity (unacceptable)

If the intensity changes within one day, the maximum intensity of the AE during that day shall be recorded.

# 7.2.5.3.2 Causal relationship and seriousness

Each AE, serious as well as non-serious, shall be assessed by the Investigator for causal relationship with the study product and its use (the injection procedure) and for seriousness (Yes or No) of the event.

A two-point scale (Yes or No response) shall be used for the causality assessments. The Investigators shall be asked to indicate a response to each of the following questions in the eCRF:

- "Do you consider that there is a reasonable possibility that the event may have been caused by the study product?", and
- "Do you consider that there is a reasonable possibility that the event may have been caused by the study product injection procedure?"

If any of these questions is answered Yes, the AE is considered related.

Each AE will also be assessed for causal relationship and seriousness by the Sponsor, in order to fulfil regulatory requirements.

In addition, each SAE will be classified by both the Investigator and Sponsor separately, according to four different levels of causality:

- 1. **Not related** Relationship to the device, comparator or procedures can be excluded when:
  - the event has no temporal relationship with the use of the investigational device, or the procedures related to investigational device;
  - the serious adverse event does not follow a known response pattern to the medical device (if the response pattern is previously known) and is biologically implausible;
  - the discontinuation of medical device application or the reduction of the level of activation/ exposure when clinically feasible and reintroduction of its use (or increase of the level of activation/exposure), do not impact on the serious adverse event;
  - the event involves a body-site or an organ that cannot be affected by the device or procedure;
  - the serious adverse event can be attributed to another cause (e.g. an underlying or concurrent illness/ clinical condition, an effect of another device, drug, treatment or other risk factors);
  - the event does not depend on a false result given by the investigational device used for diagnosis, when applicable;

> In order to establish the non-relatedness, not all the criteria listed above might be met at the same time, depending on the type of device/procedures and the serious adverse event.

Print date:

2021-08-25 16:18

- 2. Possible The relationship with the use of the investigational device or comparator, or the relationship with procedures, is weak but cannot be ruled out completely. Alternative causes are also possible (e.g. an underlying or concurrent illness/ clinical condition or/and an effect of another device, drug or treatment). Cases where relatedness cannot be assessed, or no information has been obtained should also be classified as possible.
- 3. Probable The relationship with the use of the investigational device or comparator, or the relationship with procedures, seems relevant and/or the event cannot be reasonably explained by another cause.
- 4. Causal relationship the serious adverse event is associated with the investigational device, comparator or with procedures beyond reasonable doubt when:
  - the event is a known side effect of the product category the device belongs to or of similar devices and procedures;
  - the event has a temporal relationship with investigational device use/application or procedures;
  - the event involves a body-site or organ that
    - othe investigational device or procedures are applied to;
    - othe investigational device or procedures have an effect on;
  - the serious adverse event follows a known response pattern to the medical device (if the response pattern is previously known);
  - the discontinuation of medical device application (or reduction of the level of activation/ exposure) and reintroduction of its use (or increase of the level of activation/exposure), impact on the serious adverse event (when clinically feasible);
  - other possible causes (e.g. an underlying or concurrent illness/ clinical condition or/and an effect of another device, drug or treatment) have been adequately ruled out;
  - harm to the subject is due to error in use;
  - the event depends on a false result given by the investigational device used for diagnosis, when applicable;

In order to establish the relatedness, not all the criteria listed above might be met at the same time, depending on the type of device/procedures and the serious adverse event.

#### 7.2.5.4 Reporting of adverse events

AE reporting on each subject shall start upon first treatment. All other events that occur after the subject signs the ICF but before enrollment will be recorded in the subject's medical history. The reporting shall continue during each follow-up visit (including telephone contacts and extra visits between planned visits) until the last scheduled visit in the study.

2021-08-25 16:18

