### 5.2 **Subject Identification Number**

Prior to any study procedures being conducted, the subject must sign the ICF. Each subject will be assigned a subject number that will be allocated in ascending order within each study center. A screen failure is a subject who signed the ICF but never enrolled (i.e. received treatment) in the study. For screen failures, the subject source documents should indicate which assessments have been made and the reason why the subject was determined to be a screen failure. A screen failure should not be re-entered in the study. For the duration of the clinical study, each subject will be identified using the subject number for all documentation and discussion.

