## 6.1.3 Additional products and materials

Needles for injection, 25G 1.5-inch BD needles, will be supplied by the Sponsor. The needle is approved for use in Canada.

The following will be supplied by the study centers:

- Sterile Water for Injection (SWFI), USP, 20 mL
- Single-use 5 mL sterile syringes
- Single-use 20 mL sterile syringes
- Fluid Dispensing Connector
- Single-use 1 mL sterile syringe
- 18 G sterile needles
- Single-use 3-5 mL (depending on Investigator's preference) sterile syringes
- Antiseptic
- Lidocaine HCl 2%

(Note: The reconstituted study product contains lidocaine, but additional topical or local anesthesia may be used at the discretion of the Treating Investigator before the treatment. If additional anesthesia is used, potential local anesthesia toxicity should be taken into consideration. The maximum allowable safe dose of lidocaine is 3-4.5 mg/kg. Type of anesthesia, administration route, product name, and quantity used must be recorded in the eCRF.)

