## 7.2.5 Adverse events

#### 7.2.5.1 Definition of an adverse event (AE) (Medical Devices Regulation (MDR) article 2(57))

An AE is any untoward medical occurrence, unintended disease or injury, or untoward clinical signs (including abnormal laboratory findings) in subjects, users or other persons, in the context of a clinical investigation, whether or not related to the Investigational device.

This definition includes:

- a) events related to the investigational product or the reference product
- b) events related to the procedures involved
- c) events that are anticipated as well as unanticipated

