8.1 Adverse Events

All adverse events (AEs) will be assigned to a PT and will be classified by Primary SOC according to MedDRA version 24.1 or later.

Any AE which started at or after the first administration of study treatment will be considered as Treatment Emergent Adverse Event (TEAE). If the start date is missing for an AE, the AE will be considered to be treatment emergent. Missing classifications concerning study treatment relationship will also be considered as treatment-related.

A summary of all AEs, will be provided, which will include:

- Number of subjects with at least one AE and number of events (in total as well as serious AEs)
- Number of subjects with at least one related AE and number of events (in total as well as serious AEs)
- Number of subjects with at least one unrelated AE and number of events (in total as well as serious AEs)
- Number of subjects who did not have an AE

The number of subjects with AEs related to study product or injection procedure as well as the number of events will be summarized by SOC, PT, and maximum intensity. In addition, for related AEs the number of days to onset and the duration of event will be summarized by SOC and PT. Action taken for related AEs will also be summarized. Serious AEs will be listed as well as related AEs with late onset (>21 days after most recent treatment).

Non-related AEs will be summarized by SOC, PT, and maximum intensity.

Events that occurred before the first administration of study treatment are included as Medical History.

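### AE recording starts at the first Sculptra administration, so a reaction to optional anesthesia given just before it is medical history at session 1 but an AE at sessions 2 and 3

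*Protocol*

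**What the plan says.** Protocol 7.2.5.4 sets the start of collection: "AE reporting on each subject shall start upon first treatment". It continues: "All other events that occur after the subject signs the ICF but before enrollment will be recorded in the subject's medical history". Protocol 5.2 shows what enrollment means: "A screen failure is a subject who signed the ICF but never enrolled (i.e. received treatment) in the study".

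SAP 8.1 applies the same boundary. Events with onset at or after the first administration are treatment-emergent, and for the rest: "Events that occurred before the first administration of study treatment are included as Medical History".

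Protocol 6.1.3, like the synopsis, notes that the reconstituted product already contains lidocaine but that "additional topical or local anesthesia may be used at the discretion of the Treating Investigator before the treatment". It adds a caution about local anesthetic toxicity.

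The AE definition in Protocol 7.2.5.1 is broad. It covers an untoward occurrence "whether or not related to the Investigational device" and expressly includes "events related to the procedures involved".

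At Visit 2a, Protocol 4.5.2 lists an AE evaluation only for the period after treatment.

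**The concern.** At Visit 2a a woman may be given an anesthetic as part of the treatment session before any Sculptra is injected. That is an exposure with its own risk: Protocol 2.3 says lidocaine can, in rare cases, cause allergic reactions. Known hypersensitivity to lidocaine or other local or topical anesthetics is an exclusion criterion. The reactions still possible are therefore mainly previously unknown ones, and session 1 is the first occasion in the study on which they could appear. Yet session 1 is the only session at which the interval between anesthetic and injection lies outside the AE window.

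Two things are at stake. The same procedure-related event is classified differently by session, so AE counts by session would not be like for like. And an event serious enough to stop the first injection would occur in a woman whom the planned safety tables do not cover.

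**Working it through.** The plan states no figure on this point, so the check is a comparison of the relevant rules.

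**1. Where the window opens.** Protocol 7.2.5.4 opens it at first treatment. Protocol 5.2 equates enrollment with having received treatment. SAP 8.1 uses first administration of study treatment. Together these place the start at the first Sculptra injection.

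**2. What can precede it.** The synopsis and Protocol 6.1.3 place the optional extra anesthesia before the treatment, and so before the window opens at session 1.

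**3. The same event at each session.** Take a reaction with onset after the anesthetic and before the injection.

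| Session | AE window | Classification as written |
|---|---|---|
| 1 (Visit 2a) | Not yet open | Medical history |
| 2 (Visit 3a) | Open since session 1 | AE |
| 3 (Visit 4a) | Open since session 1 | AE |

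The window stays open because Protocol 7.2.5.4 continues reporting until the last scheduled visit. At sessions 2 and 3 the event meets the definition in 7.2.5.1 whether or not it is related to the device.

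**4. If the first injection is cancelled.** The woman has not received treatment, so under Protocol 5.2 she is a screen failure. The Safety set requires injection in at least one thigh (Protocol 8.2, SAP 5.4.1), so she is outside it. SAP 8 summarizes safety for the Safety set, and SAP 6.5 summarizes medical history for the same set. SAP 6.2 tabulates screen failures by center and by criteria not met, which would not describe an anesthetic reaction. Her source documents should give the reason for screen failure, but no planned safety table would show the event.

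**5. What is not affected.** A reaction that begins after the first injection, including one to the lidocaine in the reconstituted product, is inside the window. If no extra anesthesia is used, the gap does not arise.

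**6. Scale.** Assume about 30 women and equal anesthetic use at every session.

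- If all have three sessions: 3 × 30 = 90 sessions, and session 1 is 30/90 = 33% of them.
- If all stop after one: 30/30 = 100%.

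These are shares of sessions, not of reactions. They bound how much pre-injection anesthetic exposure lies outside the window under that assumption, and they do not measure bias. The documents give no rate of anesthetic use or of reactions, so no expected number of missed events can be calculated.

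**The case against.** The strongest reply is that treatment can mean the whole session. Protocol 6.3.1, on the treatment procedure, describes skin cleaning, extra anesthesia or ice, and injection together. In the Schedule of Assessments the AE mark at Visit 2a carries no pre- or post-treatment footnote, although other items at that visit do. Protocol 7.2.5.3 asks for AE questioning at every visit after screening. On that reading there is no gap. It remains possible, but the wording in the synopsis, in 6.1.3, in 4.5.2 and above all in SAP 8.1 points to the narrower reading. The ambiguity is itself a reason to clarify.

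Three stronger inferences are tempting, and the documents do not support them.

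- **That the AE definition and the reporting start contradict each other.** A definition says what counts and a window says when collection begins, so the two can coexist. The protocol and SAP also agree on the window. What stands is the unequal handling of identical events across sessions.
- **That serious reactions drop out of SAE reporting.** Protocol 7.2.5.5 requires every SAE to be reported within 24 hours and sets no first-treatment limit. Against that, 7.2.5.2 defines an SAE as a kind of AE, and 7.2.5.4 says AE reporting has not yet begun. The instruction to the site is unclear, but loss is not shown.
- **That the safety endpoint is biased downward by a known amount.** One event in 30 women would be 3.3%, but a woman who is not injected is not in that denominator. Relatedness under 7.2.5.3.2 refers to the study product or its injection procedure. A reaction to separate anesthesia before any injection would probably not be called related, so the related-AE tables would change little.

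Nor would such events necessarily be excluded in practice. The AE form takes a start date without a clock time, and SAP 5.6 derives onset by subtracting dates. A Day 1 reaction entered as an AE in a woman who is then injected would have onset day 0, the same as a post-injection event. If it is entered as medical history instead, it still appears in the SAP 6.5 summary for injected women.

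**Conclusion.** The point holds as a minor inconsistency. On the literal rules, a reaction between optional anesthesia and the first injection is medical history at session 1 and an AE at sessions 2 and 3. A woman who reacts and is not injected is absent from every planned safety table. This rests on reading first treatment as first Sculptra administration, which the SAP wording favors, and on extra anesthesia being used at Visit 2a.

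The window is short and the exposure optional, and known anesthetic hypersensitivity is excluded, so the effect on the safety results is probably small. Its size cannot be estimated from the documents.

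**What to change.** Amend Protocol 7.2.5.4 so that AE and SAE recording starts with the first treatment-session procedure at Visit 2a, including any topical or local anesthesia. Change the matching boundary in SAP 8.1, covering both the treatment-emergent definition and the medical-history sentence, so that the two documents stay aligned. Reword the Visit 2a item in Protocol 4.5.2, which now refers only to AEs after treatment. Add one listing for any such event in a woman who is then not injected, kept apart from the Safety-set tables so that their denominator does not change.

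The cost is a sentence in each document, a small wording change in 4.5.2 and one listing. The downside is that a few more AEs may be recorded. The change concerns recording only and leaves the conduct of treatment as it is.

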# 7.2.5.5 Reporting of serious adverse events

The Investigator shall report any SAE to the Contract Research Organization (CRO) immediately but not later than 24 hours of awareness of the event. This initial report can be made via e-mail or submitted via the eCRF.

In case of difficulty to obtain all the required information within 24 hours, an initial report can be submitted, with the following information as a minimum, irrespective of whether some of it is regarded as preliminary:

- CTN 43CASA2006
- Subject identification (age, gender, subject number)
- Date when AE occurred
- Date when AE became serious
- Adverse event description
- Name of Investigator and original reporter (if other than Investigator)
- Name of study product
- Treatment specification

Follow-up information and data missing in the initial SAE reporting shall be gathered as soon as possible and reported to the CRO immediately, but not later than 24 hours of awareness of the new data. Complete and adequate information on each SAE is required. All attempts to obtain this information, including dates for follow-up activities, must be documented by the Investigator.

Supporting documentation to be provided with the SAE report:

- Concomitant therapies form/list
- AE form/list
- Medical history form/list
- Any other relevant supporting documentation (e.g. hospital notes, death certificate, autopsy reports etc.)

The SAE form must be signed and dated by the Investigator. If the initial 24-hour SAE report does not contain full information or if it is made without using the SAE form the fully completed and signed SAE form shall be e-mailed to the CRO. A copy of the fully completed SAE form shall be kept at the study center.

In addition, the PI shall report SAEs to RA within 72 hours of discovery and report SAEs to the responsible REB without undue delay. The PI is responsible for checking what reporting procedures are applicable for his/her REB regarding SAEs and final report of the outcome of the study and to comply with such reporting procedures during the study period.

The Sponsor is responsible for reporting to the RA according to national regulations.

CONFIDENTIAL

QMS-9581, CSP template (medical device), version 4.0

Page 48(63)

2021-08-25 16:18

Enrollment and injections at a study center will be temporarily halted if an SAE occurs for a vascular embolic event that leads to skin necrosis, vision loss, or stroke and is determined by the Investigator to be directly or possibly related to the investigational device or injection procedure, see stopping rules in section 4.1.

Following the initial SAE report from the Investigator to the CRO, the sponsor shall conduct an evaluation of the SAE and report the results of such evaluation to RA and to all reviewing ECs and participating investigators within 10 working days after the Sponsor first receives notice of the effect. Thereafter the Sponsor shall submit such additional reports concerning the effect as RA requests.

## 7.2.6 Follow-up of unresolved events ongoing at termination of the study

All serious as well as non-serious AEs with a causal relationship to the study product or treatment procedure and ongoing at study end, shall be followed up after the subject's participation in the study is over. Such events shall be followed-up after the last study visit until resolved, assessed as chronic or stable, or subject is lost to follow up. Follow-up information shall be reported on the AE follow-up form.

## 7.2.7 Follow-up of events occurring after subject termination of the study

All AEs with a causal relationship to the study products or treatment procedure that the Investigator becomes aware of, serious as well as non-serious, with onset after the study termination (subject's last study visit) shall be reported to the Sponsor. The report should as a minimum include the information described in Section 7.2.5.3. The report can be sent via e-mail according to contact details specified in Section 7.2.5.5. The events shall thereafter be followed-up until resolved, considered chronic or stable, or subject is lost to follow up.

